Note that besides Investigators [name] and [name] other ED physicians waivered to prescribe Suboxone will not be listed as key personnel according to the following definition. Individuals who are Not Key Personnel: An individual who will be interacting with research subjects during the course of a research study, but only in his/her regular non-research employment capacity. That is, ED physicians will be interacting with participants of the study only in their clinical roles as ED care providers. Additionally, the requirement that physicians perform 4 hours of CITI training as Key Personnel would significantly limit the number of ED physicians willing to be associated with critical

research on ED best practices.

Participants will be given a 3-day Starter Pack containing 12 x 2/0.5 mg films of Suboxone for a total daily dose of 8mg of buprenorphine for 3 days (i.e. 4 x 2/0.5 films each day = 12 films).

Patients in withdrawal will be given an immediate dose of two 2/0.5 mg films of Suboxone (i.e. two Suboxone films containing 2mg of buprenorphine and 0.5mg of naloxone each) from the Starter Pack and instructions to take two more 2/0.5mg films at home the same day for a total daily dose of 8mg of buprenorphine. Patients not manifesting withdrawal, but with presentation and history consistent with moderate to severe OUD, will be instructed to take the first two films of Suboxone from the Starter Pack when experiencing mild to moderate withdrawal symptoms, and to take another two films if symptoms persist 1-2 hours after taking the first two films. Patients will be given a written explanation of the rationale for the induction process and the risk of precipitated withdrawal if Suboxone is taken when not experiencing withdrawal symptoms (see attached "Home Induction Instructions"). Participants will receive detailed verbal instructions in addition to a written self-medication guide.⁴⁴

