Participants will also receive in the Starter Pack Suboxone for two additional days of treatment (i.e. the remaining 8 films containing 2/0.5mg Suboxone with instructions to take 4 films on day 2 and the remaining 4 films on day 3). The additional Suboxone doses will accommodate those entering the study on the weekend because the ATP only accepts new patients during week days (i.e. Monday to Friday). Participants are instructed to bring any extra doses with them to the first appointment at the ATP which will be incorporated into the maintenance prescription provided at the ATP. Research and clinical experience indicate that many patients will require daily doses of buprenorphine greater than 8mg to fully suppress craving and withdrawal, and for these patients dose escalation will be available under medical supervision when starting treatment at ATP. The initial 8mg dose limit is for self-administered doses only, to provide immediate relief of withdrawal symptoms and craving while limiting potential for excessive dosing or diversion.⁴⁴⁻⁴⁸

Potential for Medication Diversion. To reduce the potential for drug diversion, individuals will be allowed to enroll only once in the present study. Treatment initiation at ED will start with a dose sufficient to diminish withdrawal and craving but less than has been used in previous studies of linkage to treatment or home induction. e.g. ^{45,49} Rapid follow-up including upward adjustment of dose if needed under medical supervision will be provided at the bridge clinic or the local MAT provider

The range of dates (i.e. week period around 3 and 6 months after randomization) for the last two follow-up visits will be written down and given to participants with other study materials at the initial ED visit. Participants will be told that they will be contacted in the week before the follow-up visits at 3 and 6 months to arrange the specific time and place of the follow-up visit.

Step 11. Collection of additional information will occur by phone within seven days of randomization. This will include psychiatric history assessed by the 15 minute Mini-International Neuropsychiatric Interview (MINI),^{37,38} opioid use history (e.g. onset, duration of use, route of administration) assessed with the Pattern of Substance Use -Adult questionnaire in the PhenX toolkit, and the GPRA Client Outcome Measures questionnaire. Data will be collected on an iPad.

Part 4) Referral

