Part 5) Outcome Assessment. The primary outcome will be illicit opioid use at 1 week and 3 & 6 months after buprenorphine induction. Consistent with standard ATP practice, urine sample collection and analysis will be performed by Aspenti Labs (<https://www.aspenti.com/>), a clinical drug testing service which is open Monday to Friday 7AM-7PM and has multiple locations throughout Vermont. Urine specimens will be collected under observation of same-sex staff and analyzed for opioids (buprenorphine, methadone, oxycodone, hydrocodone, hydromorphone, heroin, fentanyl) and other drugs (cocaine, amphetamines, benzodiazepines, cannabinoids) via enzyme multiplied immunoassay. Missing urine specimens will be considered positive for illicit opioids, consistent with an intent-to-treat approach. Additional outcomes will include self-reported illicit opioid or other (non-opioid) drug use, treatment enrollment status and behavioral questionnaires (i.e. the GPRA Client Outcome Measures questionnaire to track self-reported drug-use and life conditions). The Treatment Effectiveness Assessment (TEA)⁴³ will be included at 1 week, 3 months and 6 months to track patient perception of treatment progress. Additional follow-up questions based on the PhenX toolkit are attached.

Retention. Participating in OUD treatment has health advantages for the participants which is a motivation to remain in the study. Participants will receive a \$25 gift card after answering questionnaires in Step 11. In addition, as an incentive to provide a urine sample and answer questions at follow-up, participants will receive a \$25 gift card for answering questions by phone and a \$50 gift card for a urine sample at each of the three outcome time points completed (i.e. 1 week, 3 and 6 months post randomization). In total, participants can earn up to \$250 for their participation in the study. To avoid altering the motivation to stay in MAT, participants will earn payment for providing the urine samples and answering questions at each of the 3 follow-up time points, regardless of whether they are currently in treatment. Missing urine specimens will be considered positive for illicit opioids, consistent with an intent-to-treat approach.

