Participants will be contacted by phone, text and/or email. A letter will also be mailed to participants (see attached). In the event the participant cannot be reached by any other means, a letter will be sent to the contact person provided by the participant at intake on the Locator Form. Contact information for phone, text and email will be collected at the initial ED visit. The dates (i.e. 1 week, 3 months and 6 months after randomization) for the follow-up visits will be written down and given to participants with other study materials during the initial ED visit. Participants will be contacted in the week before the follow-up visits at 3 and 6 months to remind them of the date and answer any question about where and how urine samples will be collected. Participants will also be reminded again the day before.

For research involving survey, questionnaires, etc.: Describe the setting and the mode of administering the instrument and the provisions for maintaining privacy and confidentiality. Include the duration, intervals of administration, and overall length of participation. (describe and attach all instruments)

Not applicable

Behavioral questionnaires will be used to assess participants at the following time points.

At baseline, participants will be assessed using the Locator Form, Referral, Suicidality, GPRA, MINI Neuropsychiatric Interview, Why are you enrolling in this program: Prevent overdose/Want to be sober/Family pressure/Legal pressure/Job pressure/Other. Total duration 1 hour.

At week 1, participants will be complete the MINI questionnaire Part II. Total duration 25 minutes.

At 3 months, participants will be assessed using a modified version of the PhenX drug use toolkit, the TEA and attached follow-up questionnaire and the GPRA. Total duration 25 minutes.

At 6 months, participants will be assessed using a modified version of the PhenX drug use toolkit, the TEA and attached follow-up questionnaire based on the PhenX toolkit Total duration 35 minute.

At 3 and 6 month follow-up:

1. Since you received buprenorphine (suboxone) in the ED have you taken any more buprenorphine prescribed for you by a doctor or other prescriber? (If No, skip to item 3)
2. If you answered yes to #1: are you currently (last 30 days) enrolled in treatment with a prescriber?
3. If you are not currently receiving suboxone from a prescriber, why?

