4. Since you started receiving treatment in the ED have you experienced any of the following side effects of buprenorphine? (Constipation, diarrhea, stomach pain, nausea, vomiting, brain fog, sleeping too little, tiredness, sexual problems, feeling depressed or down, feeling anxious, headache)

If yes follow up with: How much discomfort did this cause you on a scale 1 to 5 where 1 is mild and 5 is severe?

5. Have you been doing more of any of the following since starting treatment in the ED:

Have you been eating more than before you started treatment?

Have you been drinking caffeine more than before you started treatment?

Have you been smoking more cigarettes or other nicotine products more than before you started treatment?

Have you been using more marijuana than before you started treatment?

Have you been drinking more alcohol than before you started treatment?

Have you been using other drugs more than before you started treatment? If yes, which ones?

Have you been spending more time online than before you started treatment?

Have you been gambling more than before you started treatment?

Have you been having more sex than before you started treatment?

Have you been exercising more than before you started treatment?

Any other activities? If yes, what are they?

6. How often over the last two weeks have you been bothered by not being able to stop or control how much you eat?

How often over the last two weeks have you been bothered by how much caffeine you drink?

How often over the last two weeks have you been bothered by how many cigarettes you smoke or use other nicotine products?

How often over the last two weeks have you been bothered by how much marijuana you use?

How often over the last two weeks have you been bothered by how much alcohol you drink?

How often over the last two weeks have you been bothered by how much other drugs you use? If yes, which ones?

How often over the last two weeks have you been bothered by how much time you spend online?

How often over the last two weeks have you been bothered by how much time spent gambling?

How often over the last two weeks have you been bothered by how much time spent having sex?

How often over the last two weeks have you been bothered by how much time spent exercising?

Individual questionnaire durations are as follows:

MINI Neuropsychiatric Interview takes approximately 15 minutes to complete.

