Risk of Accidental Exposure in Children: There is an increased chance of child exposure to buprenorphine resulting from this medical intervention. However, this should be viewed in a wider health perspective. Most medications prescribed by ED (hypoglycemics, CCBs, BBs, cholchicine, other opioids, etc) are dangerous in exploratory ingestions and many of these are on the “one pill can kill” list for kids. It is likely the adults who will receive a Suboxone Starter Pack have opioids in the home already. In fact, the study is attempting to trade illicit use (e.g. heroin/fentanyl) for a safer opioid which should lead to improved adult supervision of children and reduce risk of parental death by overdose. The benefits to families of treating the disease appear to outweigh the risks.

Risks from Opioid Withdrawal: Opioid withdrawal symptoms which include tearing up, muscle aches, agitation, trouble falling and staying asleep, excessive yawning, anxiety, nose running, sweats, racing heart, hypertension, nausea and vomiting, diarrhea, stomach cramps, depression and drug cravings. Symptoms of withdrawal will be managed with buprenorphine. Participants will be educated about opioid withdrawal with a fact sheet that includes a brief list of coping strategies. If participants still experience opioid withdrawal after buprenorphine induction, research staff will cue the participant to use coping strategies. Clinical support will be provided by addiction psychiatrists at the ATP.

Risks from Research Assessments: The assessments being used in this study (e.g. measures of substance use, symptoms, information about patient history, and urine assessments) may cause some discomfort, boredom, anxiety or fatigue. Participants will be advised that they can take a break, refuse to answer question(s), or end the study session if they become uncomfortable in any way. Additionally, psychiatrists experienced in the treatment of addiction, will be present or rapidly available via pager for emergency consultation at any time.

Risk Related to Confidentiality: This research involves monitoring and treatment of patients who use illicit opioids. Participants may engage in other illegal drug use activities. Maintaining confidentiality is an area of utmost importance for this population.

Protections Against Risks

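### The only structured side-effect question is asked at 3 and 6 months; the week-1 call, about 4 days after the take-home pack ends, has no described safety item

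*Combined protocol and SAP*

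**What the plan says.** **Exposure and named risks.** Part 2 (Buprenorphine Induction) supplies 12 films, four a day. Patients already in withdrawal receive their first two films straight away and take the rest at home. The others start by themselves once withdrawal symptoms appear, with written material on "the risk of precipitated withdrawal if Suboxone is taken when not experiencing withdrawal symptoms". The Risks section adds: "There is an increased chance of child exposure to buprenorphine resulting from this medical intervention". The Toxicity entry under Drug and Device Information discusses respiratory depression with intravenous buprenorphine, and coma and death when intravenous misuse is combined with benzodiazepines.

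**Structured questions.** Three places describe the early research contacts:
- The questionnaire time points in Methods and Procedures: "At week 1, participants will be complete the MINI questionnaire Part II".
- Part 5 (Outcome Assessment): the TEA "will be included at 1 week, 3 months and 6 months to track patient perception of treatment progress".
- Step 11: "Collection of additional information will occur by phone within seven days of randomization". Its content is the MINI, opioid-use history and the GPRA.

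The side-effect question, item 4, stands under "At 3 and 6 month follow-up" and begins "Since you started receiving treatment in the ED have you experienced any of the following side effects of buprenorphine". It lists 12 symptoms, each with a 1-to-5 discomfort rating.

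**Other safety provisions.** Data Safety and Monitoring covers adverse events that participants report or staff notice. These go to key personnel within 24 hours, serious events go to the IRB, and all are reviewed every six months. The Risks section also states: "If participants still experience opioid withdrawal after buprenorphine induction, research staff will cue the participant to use coping strategies".

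**The concern.** The harms particular to a take-home induction pack are expected in the first days. A question first put three months later relies on long recall. Without onset dates, its answers cannot be tied to the induction days. Several of the early harms are not on the list at all.

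Two things are at stake. First, the protocol says positive findings on Aim 1 will support adoption across the Vermont network. Adopters would want to know how the induction itself was tolerated. Second, where structured collection is late, early events reach the study through clinical contact or unprompted reports, and the two groups differ in how close their clinicians are to the study. A difference in recorded events could then reflect a difference in ascertainment.

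**Working it through.** The plan gives no figure to reproduce. The check compares the schedule with the exposure, using simple subtraction.

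**1. Length of exposure.** 12 films ÷ 4 per day = 3 days, so the pack ends on day 3 if started on the ED day.

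**2. Recall gap = day of question − day 3.** Week 1 is taken as day 7, 3 months as about day 91 and 6 months as about day 183.

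| Contact | Day | Gap after pack ends | Side-effect item described? |
|---|---|---|---|
| Week 1 | 7 | 7 − 3 = 4 days | No |
| 3 months | 91 | 91 − 3 = 88 days | Yes, item 4 |
| 6 months | 183 | 183 − 3 = 180 days | Yes, item 4 |

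A participant who starts the pack later has every gap shortened by the same delay. Week 1 still comes 91 − 7 = 84 days before the 3-month call.

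**3. What item 4 can show.** It looks back to the start of ED treatment, so it covers the induction days, but it collects no onset dates. Seven of its 12 terms also appear in the protocol's own list of withdrawal symptoms: diarrhea, stomach pain (there, cramps), nausea, vomiting, poor sleep, low mood and anxiety. A positive answer at 3 months therefore does not separate a reaction to the first dose from a later medication effect or later withdrawal.

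**4. What item 4 does not name.** Precipitated withdrawal, overdose, breathing problems and child exposure are absent. The nearest term to sedation is tiredness.

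**5. Room on the week-1 call.** The listed duration is 25 minutes. The MINI takes 15 and the TEA 5, so 25 − (15 + 5) = 5 minutes are not attributed to any instrument. The full MINI time is used here because none is given for Part II.

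**6. Consistency of the early content.** The time-point list gives MINI Part II alone for week 1, Outcome Assessment adds the TEA, and Step 11 has a phone collection within the same seven days that includes the GPRA. The GPRA takes about 30 minutes by itself, longer than the whole week-1 slot, so the text does not settle what is asked at which call.

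**7. The cueing statement.** Research staff are to cue coping strategies if withdrawal persists after induction. The schedule describes no research contact during the induction days that asks about withdrawal, so the text does not show at which contact this would arise.

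**The case against.** The strongest reply is that early harms have several ways of being found, and most of it stands.

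- **Bridge-clinic group.** The opening section guarantees ATP enrollment within 24 to 72 hours, at about the end of the pack. The ATP entry stage then has weekly physician visits at which doses are adjusted for persisting withdrawal symptoms. This applies to the 140 of 200 participants expected at UVMMC, apart from those who do not attend.
- **Direct-referral group.** A reader might infer that these participants have no route for reporting early harms. The documents do not support that. The paragraph on medication diversion provides rapid follow-up at the bridge clinic or the local provider, and procedures at the two other sites are deferred to later amendments. What is missing so far is a described path from local providers to the study's records.
- **Spontaneous reporting.** An event mentioned on the week-1 call would enter the adverse-event process. It would depend on the participant raising it.
- **Item 4's look-back.** A reader might infer that the trial will have no information on harms in the induction days. That goes too far, because item 4 reaches back to the ED visit and rates discomfort. The fair criticism is late recall, no dates and missing terms.
- **The cueing statement.** A reader might infer that this protection can never operate. A participant may raise withdrawal with staff or a clinician, so the documents support only a request to reconcile it with the contact schedule.
- **Unseen instruments.** The questionnaires are attachments that were not available. An unlisted week-1 safety item is possible, and 5 minutes of the call are unexplained.
- **Not the study contrast.** Both groups receive ED-initiated buprenorphine and safety is not a stated objective, so Aim 1 is unaffected.

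These points narrow the concern. They do not replace a uniform early question.

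**Conclusion.** The point holds in a limited form. As the protocol text describes it, structured side-effect collection begins about 88 days after the 3-day pack ends, is repeated at about 180 days, has no onset dates, and omits by name several early harms, including ones the protocol itself discusses. Earlier capture exists but is passive or clinical. It is likely to be fuller for bridge-clinic participants because the Data Safety and Monitoring section places their ATP psychiatrists on the study team. The size of any resulting imbalance cannot be estimated from the documents.

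This is a worthwhile, inexpensive improvement to safety data and does not threaten the primary analysis. It rests on the calendar-day conversions shown above, and on the text being complete about what is asked at week 1. If an attached instrument already asks about side effects then, what remains is to say so in the schedule and to check which harms it names.

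**What to change.** 1. Ask item 4 at the existing week-1 call as well, with a look-back to the first dose and an onset date for each symptom. Keep it at 3 and 6 months.
2. Add short yes/no items on: withdrawal that worsened after a dose; overdose or naloxone use; excessive sedation or breathing trouble; unplanned ED visit or admission; and exposure of a child or other person to the films.
3. Ask these in the same words in both groups, and write them into the amendments for the two referral sites. Handle positive answers under the reporting process already in Data Safety and Monitoring. No new clinical rule is proposed.
4. Reconcile the early-contact content across Step 11, Outcome Assessment and the questionnaire time points, and reconcile the cueing statement in the Risks section with the contact schedule.

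The cost is one questionnaire amendment and a few more minutes on a call that is already scheduled, staffed and compensated. The first recall gap falls from about 88 days to about 4.
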